5. STUDY POPULATION

Male and non-pregnant female adults ≥ 18 years of age or older with COVID-19 and who meet all eligibility criteria will be enrolled at up to approximately 100 clinical trial sites globally. The target population should reflect the community at large. The estimated time from screening (Day -1 or Day 1) to end of study for an individual subject is approximately 29 days.

Subject Inclusion and Exclusion Criteria must be confirmed by any clinician named on the delegation log. If there is any uncertainty, the PI should make the decision on whether a potential subject is eligible for study enrollment. There is no exclusion for receipt of SARS-CoV-2 vaccine (experimental or licensed).

5.1 Inclusion Criteria

Appendix B - ACTT-2: Baricitinib/Remdesivir vs Remdesivir

1. Admitted to a hospital with symptoms suggestive of COVID-19.
2. Subject (or legally authorized representative) provides informed consent prior to initiation of any study procedures.
3. Subject (or legally authorized representative) understands and agrees to comply with planned study procedures.
4. Male or non-pregnant female adults ≥ 18 years of age at time of enrollment.
5. Has laboratory-confirmed SARS-CoV-2 infection as determined by PCR or other commercial or public health assay in any specimen, as documented by either of the following:
 - PCR positive in sample collected < 72 hours prior to randomization; OR
 - PCR positive in sample collected ≥ 72 hours prior to randomization, documented inability to obtain a repeat sample (e.g. due to lack of testing supplies, limited testing capacity, results taking > 24 hours, etc.) AND progressive disease suggestive of ongoing SARS-CoV-2 infection.
6. Illness of any duration, and at least one of the following:
 - Radiographic infiltrates by imaging (chest x-ray, CT scan, etc.), OR
 - $SpO_2 \leq 94\%$ on room air, OR
 - Requiring supplemental oxygen, OR
 - Requiring mechanical ventilation or ECMO.
7. Women of childbearing potential must agree to either abstinence or use at least one primary form of contraception not including hormonal contraception from the time of screening through Day 29.
8. Agrees to not participate in another clinical trial for the treatment of COVID-19 through Day 29.

5.2 Exclusion Criteria

1. ALT or AST > 5 times the upper limit of normal.
2. Estimated glomerular filtration rate (eGFR) < 30 ml/min or patient is receiving hemodialysis or hemofiltration at time of screening.
3. Neutropenia (absolute neutrophil count < 1000 cells/ μ L) ($< 1.0 \times 10^3/\mu$ L or < 1.0 GI/L).
4. Lymphopenia (absolute lymphocyte count < 200 cells/ μ L) ($< 0.20 \times 10^3/\mu$ L or < 0.20 GI/L)
5. Pregnancy or breast feeding.
6. Anticipated discharge from the hospital or transfer to another hospital which is not a study site within 72 hours.
7. Allergy to any study medication.
8. Received three or more doses of remdesivir, including the loading dose, outside of the study under the EUA (or similar mechanism) for COVID-19.
9. Received convalescent plasma or intravenous immunoglobulin [IVIg]) for COVID-19, the current illness for which they are being enrolled.
10. Received small molecule tyrosine kinase inhibitors (e.g. baricitinib, imatibib, genfinitib), in the 1 week prior to screening

Appendix B - ACTT-2: Baricitinib/Remdesivir vs Remdesivir

11. Received monoclonal antibodies targeting cytokines (e.g., TNF inhibitors, anti-interleukin-1 [IL-1], anti-IL-6 [tocilizumab or sarilumab]), or T-cells (e.g., abatacept) in the 4 weeks prior to screening.
12. Received monoclonal antibodies targeting B-cell (e.g., rituximab, and including any targeting multiple cell lines including B-cells) in the 3 months prior to screening.
13. Received other immunosuppressants in the 4 weeks prior to screening and in the judgement of the investigator, the risk of immunosuppression with baricitinib is larger than the risk of COVID-19.
14. Received ≥ 20 mg/day of prednisone or equivalent for ≥ 14 consecutive days in the 4 weeks prior to screening.
15. Use of probenecid that cannot be discontinued at study enrollment.
16. Have diagnosis of current active tuberculosis (TB) or, if known, latent TB treated for less than 4 weeks with appropriate anti-tuberculosis therapy per local guidelines (by history only, no screening required).
17. Suspected serious, active bacterial, fungal, viral, or other infection (besides COVID-19) that in the opinion of the investigator could constitute a risk when taking investigational product.
18. Have received any live vaccine (that is, live attenuated) within 4 weeks before screening, or intend to receive a live vaccine (or live attenuated) during the study. Note: Use of non-live (inactivated) vaccinations is allowed for all subjects.
19. Have a history of VTE (deep vein thrombosis [DVT] or pulmonary embolism [PE]) within 12 weeks prior to screening or have a history of recurrent (>1) VTE (DVT/PE).
20. Immunocompromised patients, patients with a chronic medical condition, or those taking a medication that cannot be discontinued at enrollment, who, in the judgment of PI, are at increased risk for serious infections or other safety concerns given the study products.

5.2.1 Exclusion of Specific Populations

Children and adolescents will not be included in this trial. Remdesivir has only been used in a small number of pediatric patients. Baricitinib has been used extensively in pediatric patients. Initial information about the epidemiology of COVID-19 indicates that the overwhelming burden of severe disease occurs among older adults, especially those with comorbidities. Given significant gaps in knowledge in this population, and a low incidence of severe morbidity/mortality in children, and that neither drug has demonstrated efficacy in COVID-19, this research is not known to have the prospect of direct benefit to individual child participants, and the risk/benefits do not warrant inclusion of this population into this trial at this time.

In nonclinical reproductive toxicity studies, remdesivir demonstrated no adverse effect on embryo-fetal development when administered to pregnant animals. Embryonic toxicity was seen when remdesivir was initiated in female animals prior to mating and conception, but only at a systemically toxic dose. Remdesivir has not been studied in pregnant women. While baricitinib is a licensed drug with a known safety profile, the limited human data on use of baricitinib in pregnant women are not sufficient to inform a drug-associated risk for major birth defects or miscarriage. Because the effects on the fetus and the pregnant woman are not fully known, pregnant women will not be eligible for the trial.

Appendix B - ACTT-2: Baricitinib/Remdesivir vs Remdesivir

In animal studies, remdesivir metabolites have been detected in the nursing pups of mothers given remdesivir. It is not known whether remdesivir is secreted in human milk. Because the effects of remdesivir on the breastfeeding infant is not known, women who are breast feeding will not be eligible for the trial.

There is no information available on the presence of baricitinib in human milk or the effects of the drug on the breastfed infant. Baricitinib is present in the milk of lactating rats. However, the clinical relevance of these data is not clear. Because of the potential for serious adverse reactions in nursing infants, women who are breast feeding will not be eligible for the trial.

5.3 Inclusion of Vulnerable Subjects

Certain human subjects are categorized as vulnerable populations and require special treatment with respect to safeguards of their well-being. For this clinical trial, examples include cognitively impaired or mentally disabled persons and intubated individuals who are sedated. When it is determined that a potential research subject is cognitively impaired, federal and institutional regulations permit researchers to obtain consent from a legally authorized representative (LAR). The study team will obtain consent from these vulnerable subjects using an IRB-approved protocol- specific process for consent using a LAR.

For subjects for whom a LAR gave consent, during the course of the study, if the subject regains the capacity to consent, informed consent must be obtained from the subject and the subject offered the ability to leave the study if desired.

5.4 Lifestyle Considerations

During this study, subjects are asked to:

- Refrain from drinking alcohol through Day 15.
- Avoid getting pregnant during the study from Day 1 through Day 29.
- Agreed not to participate in another clinical trial for the treatment of COVID-19 or SARS-CoV-2. This includes interventional trials that evaluate treatment of SARS-CoV-2 infection as well as the disease pathogenesis (e.g., experimental treatment trials for the COVID-19-related thrombo-occlusive disease respiratory complications and dysregulated immune response to the virus). Co-enrollment for natural history studies of COVID-19, studies of SARS-CoV-2 diagnostics, or strategy trials comparing different standards of care for non-COVID treatment (i.e. comparing two VTE prophylaxis regimens) is permitted; however, participation in both ACTT and these studies can only occur if the recommended blood collection volumes are not exceeded.

5.5 Screen Failures

Following consent, after the screening evaluations have been completed, the investigator or designee is to review the inclusion/exclusion criteria and determine the subject's eligibility for the study. If there is any uncertainty, the PI should make the decision on whether a potential subject is eligible for study enrollment.

Only basic demographic information and the reason(s) for ineligibility will be collected on screen failures. Subjects who are found to be ineligible will be told the reason(s) for ineligibility.

Individuals who do not meet the criteria for participation in this study (screen failure) because of an abnormal laboratory finding may be rescreened once.

5.6 Strategies for Recruitment and Retention

5.6.1 Recruitment

It is anticipated that patients with COVID-19 will present to participating hospitals, and that no external recruitment efforts towards potential subjects are needed. Recruitment efforts may also include dissemination of information about this trial to other medical professionals / hospitals.

The IRB will approve the recruitment process and all materials provided prior to any recruitment to prospective subjects directly.

Screening will begin with a brief discussion with study staff. Some will be excluded based on demographic data and medical history (i.e., pregnant, < 18 years of age, renal failure, etc.). Information about the study will be presented to potential subjects (or legally authorized representative) and questions will be asked to determine potential eligibility. Screening procedures can begin only after informed consent is obtained.

5.6.2 Retention

Retention of subjects in this trial is very important for determining the primary endpoint. As such, after hospital discharge, participating subjects will be reminded of subsequent study visits and every effort will be made to accommodate the subject's schedule to facilitate follow-up within the specified visit window. Additionally, there are many circumstances that influence the ability to obtain outcome information after discharge. Follow-up visits may be conducted by phone if in-person visits are not feasible.

5.6.3 Compensation Plan for Subjects

Compensation, if any, will be determined locally and in accordance with local IRB requirements, and subject to local IRB approval.

5.6.4 Costs

There is no cost to subjects for the research tests, procedures/evaluations and study product while taking part in this trial. Procedures and treatment for clinical care including costs associated with hospital stay may be billed to the subject, subject's insurance or third party.

6. STUDY PRODUCT

6.1 Study Product(s) and Administration

	Baricitinib	Placebo
Remdesivir	Arm 1 Baricitinib tablets + remdesivir IV	Arm 2 Placebo tablets + remdesivir IV

6.1.1 Study Product Description

Remdesivir is a single diastereomer monophosphoramidate prodrug designed for the intracellular delivery of a modified adenine nucleoside analog GS-441524. In addition to the active ingredient, the lyophilized formulation of remdesivir contains the following inactive ingredients: water for injection, SBECD, and hydrochloric acid and/or sodium hydroxide.

Baricitinib is a Janus kinase (JAK) inhibitor with the chemical name [1-(ethylsulfonyl)-3-(4-(7Hpyrrolo(2,3-d)pyrimidin-4-yl)-1H-pyrazol-1-yl)azetidin-3-yl]acetonitrile and will be supplied in 36 count bottles. The treatment will be allocated as one bottle per subject, with some overage per bottle. Each tablet contains 2 mg of baricitinib and the following inactive ingredients: croscarmellose sodium, magnesium stearate, mannitol, microcrystalline cellulose, ferric oxide, lecithin (soya), polyethylene glycol, polyvinyl alcohol, talc and titanium dioxide.

Placebo tablets also manufactured by Eli Lilly and Company USA, and they contain lactose monohydrate, microcrystalline cellulose, croscarmellose sodium, and magnesium stearate. The coating for the placebo tablet is identical to that of the corresponding active tablet listed above. However, there is no lactose monohydrate in baricitinib, the active oral product.

Baricitinib and placebo tablets will be supplied in 36 count bottles. The treatment will be allocated as one bottle per subject, with some overage per bottle.

6.1.2 Dosing and Administration

All subjects will receive remdesivir as a 200 mg intravenous (IV) loading dose on Day 1, followed by a 100 mg once-daily IV maintenance dose for the duration of the hospitalization up to a 10-day total course.

If subjects already received the loading dose as under the EUA or similar mechanism, then start at 100 mg/day. Any doses of remdesivir under an EUA (or similar mechanism) prior to enrollment will be counted, so the total duration of remdesivir (i.e. EUA + on this trial) is 10 days (i.e., a maximum of 10 total infusions). If one or two doses of remdesivir were administered (under EUA or similar mechanism) prior to study enrollment, this should be documented in eClinical as a concomitant medication given prior to Day 1.

For the baricitinib component, subjects will receive either active product or placebo as follows:

- Baricitinib will be administered as a 4 mg orally (po) (two 2mg tablets) or crushed for NG tube, daily for the duration of the hospitalization up to a 14-day total course.

- A placebo will be given as two tablets po or crushed for NG tube, daily for the duration of the hospitalization up to a 14-day total course.

See Section 6.1.4 for dosing modifications for renal failure.

Dosing of the two medications does not need to occur at the same.

Any dose that is delayed may be given later that calendar day. Any dose that is missed during the study due to any reason (not given that calendar day) is not made up. The treatment course continues as described above even if the subject becomes PCR negative.

Duration of therapy:

- IV remdesivir – 10 days while hospitalized (i.e., maximum of 10 total infusions pre-enrollment and during study).
- Oral (baricitinib or placebo) component – 14 days while hospitalized (i.e., maximum of 14 total doses).
- Both stop on discharge from hospital. If readmitted after discharge, see Section 7.4.

6.1.3 Dose Escalation

Not Applicable

6.1.4 Dose Modifications

The site should use all available laboratory values to evaluate for potential dose modifications. These laboratory values may be drawn as part of standard of care or protocol-required safety laboratories done as per the SOA. The protocol-required safety laboratories (per the SOA) are anticipated to be sufficient for evaluating for most dose modifications, but if other laboratory data obtained as part of standard care are available, these should be also be used in the evaluation.

Remdesivir component:

If the eGFR decreases to an eGFR < 25 ml/min, the remdesivir infusion should not be given on that day. The infusion may be resumed on the next day if the eGFR returns to ≥ 30 ml/min. If the subject's renal function worsens to the point that they require hemodialysis or hemofiltration, remdesivir will be discontinued.

If the ALT and/or AST increases to > 5 times upper limits of normal, the remdesivir infusion should be held and not be restarted until the ALT and AST ≤ 5 times upper limits of normal.

Baricitinib/Oral Placebo component:

Dose of oral study product will be decreased based on eGFR. Specifically, subjects with eGFR <60 mL/min will receive a dose of one tablet (2-mg or placebo) once daily.

Oral study product should be temporarily interrupted if the subject develops any of the following during the study but may resume when that criteria is no longer fulfilled:

- Total white blood cells (WBC) <1000 cells/ μ L
- Absolute neutrophil count (ANC) <500 cells/ μ L
- Absolute lymphocyte count (ALC) <200 cells/ μ L
- ALT or AST >5 times ULN
- Infection that, in the opinion of the investigator, merits study drug being withheld
- eGFR < 30 mL/min, resume when eGFR returns to \geq 30 mL/min.
 - If subject's renal function worsens to the point that they require hemodialysis or hemofiltration, oral study product and remdesivir as discussed above will be discontinued.

For laboratory values that meet permanent discontinuation thresholds, study product should be discontinued. However, if in the opinion of the investigator, the laboratory abnormality is due to intercurrent illness or another identified factor, laboratory tests may be repeated.

6.1.5 Overdosage

There is no known antidote for baricitinib. Overdose is not anticipated in the context of a clinical trial. However, if a site inadvertently gives a subject 4 mg of oral study product when they should be receiving 2 mg because of a eGFR <60 mg/mL, the site should contact the Sponsor. The subject should receive supportive therapy based on the subject's signs and symptoms.

6.2 Preparation/Handling/Storage/Accountability

6.2.1 Acquisition and Accountability

Investigational products (IP) will be shipped to the site either directly from participating companies, from the Sponsor, or from other regional or local drug repositories. All other supplies should be provided by the site. Multiple lots of each IP may be supplied.

Study products received at the sites will be open label and not kit specific, unless specified in the protocol-specific Manual of Procedures (MOP) or pharmacy manual. Drug preparation will be performed by the participating site's unblinded research pharmacist on the same day of administration to the subject. See the MOP Appendices for detailed information on the preparation, labeling, storage, and administration of investigational products.

Accountability:

The site PI is responsible for study product distribution and disposition and has ultimate responsibility for study product accountability. The site PI may delegate to the participating site's research pharmacist responsibility for study product accountability. The participating site's research pharmacist will be responsible for maintaining complete records and documentation of study product receipt, accountability, dispensation, storage conditions, and final disposition of the study product(s). Time of study drug administration to the subject will be recorded on the appropriate data collection form (CRF). All study product(s), whether administered or not, must be documented on the appropriate study product accountability record or dispensing log. The Sponsor's monitoring staff will verify the participating site's study product accountability

Appendix B - ACTT-2: Baricitinib/Remdesivir vs Remdesivir records and dispensing logs per the site monitoring plan. Refer to the protocol-specific MOP for details on storing study medications.

Destruction:

After the study treatment period has ended or as appropriate over the course of the study after study product accountability has been performed, used active and placebo product can be destroyed on-site following applicable site procedures with a second staff member observing and verifying the destruction.

Unused product at the end of the study should be saved until instructed by the Sponsor.

6.2.2 Formulation, Appearance, Packaging, and Labeling

Remdesivir component

The lyophilized formulation of remdesivir is a preservative-free, white to off-white or yellow, lyophilized solid containing 150 mg or 100 mg of remdesivir to be reconstituted with 29 mL or 19 mL (respectively) of sterile water for injection respectively and diluted into IV infusion fluids prior to IV infusion. Following reconstitution, each vial contains a 5 mg/mL remdesivir concentrated solution with sufficient volume to allow withdrawal of 30 mL (150 mg of remdesivir) or 20 mL (100 mg of remdesivir).

It is supplied as a sterile product in a single-use, Type 1 clear glass vial. In addition to the active ingredient, the lyophilized formulation of remdesivir contains the following inactive ingredients: water for injection, SBECD, hydrochloric acid, and/or sodium hydroxide. For more information, refer to the MOP.

Remdesivir will be labeled according to manufacturer specifications and include the statement “Caution: New Drug Limited by Federal (USA) Law to Investigational Use.”

Baricitinib component

According to the package insert, baricitinib tablets are available for oral administration as film-coated, immediate-release tablets. The 2 mg tablet is light pink and oblong. Each tablet contains 2 mg of baricitinib and the following inactive ingredients: croscarmellose sodium, magnesium stearate, mannitol, microcrystalline cellulose, ferric oxide, lecithin (soya), polyethylene glycol, polyvinyl alcohol, talc and titanium dioxide.

Oral placebo component

Placebo tablets match the active product in appearance. The placebo tablets contain lactose monohydrate, microcrystalline cellulose, croscarmellose sodium, and magnesium stearate. The coating for the placebo tablet is identical to that of the corresponding active tablet listed above. Placebo is supplied as 2 mg film-coated, in 36 count bottles, open label.

Study interventions (baricitinib and placebo) will be supplied by the sponsor or its designee in accordance with current Good Manufacturing Practice (cGMP).

6.2.3 Product Storage and Stability

Appendix B - ACTT-2: Baricitinib/Remdesivir vs Remdesivir

The Pharmacy Manual provides instructions for the preparation, handling, and storage of baricitinib drug product and placebo, and describes site responsibility and accountability for the administered products.

6.2.4 Preparation

Refer to the protocol-specific MOP for details about preparation.

Remdesivir is not considered a hazardous drug as defined by NIOSH and ASHP hazard classification systems. The study products may be prepared in a clean room but do not need to be prepared or handled in a fume hood. Baricitinib is a "Hazardous Chemical" as defined by the OSHA Hazard Communication Standard, 29 CFR 1910.1200.

Measures that minimize drug contact with the body should always be considered during handling, preparation, and disposal procedures as indicated in the IB.

6.3 Measures to Minimize Bias: Randomization and Blinding

6.3.1 Randomization

Randomization will be stratified by:

- Site
- Severity of illness at enrollment (by ordinal scale)
 - Severe disease:
 - Hospitalized, on invasive mechanical ventilation or ECMO, or
 - Hospitalized, on non-invasive ventilation or high flow oxygen devices.
 - Moderate disease:
 - Hospitalized, requiring supplemental oxygen, or
 - Hospitalized, not requiring supplemental oxygen.

The randomization procedure will be described in the MOP.

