3. OBJECTIVES AND ENDPOINTS

The overall objective of the study is to evaluate the clinical efficacy and safety of different investigational therapeutics relative to the control arm among hospitalized adults who have COVID-19.

OBJECTIVES	ENDPOINTS (OUTCOME MEASURES)
Primary	
To evaluate the clinical efficacy, as assessed by time to recovery, of different investigational therapeutics as compared to the control arm.	Day of recovery is defined as the first day on which the subject satisfies one of the following three categories from the ordinal scale: 
 • Hospitalized, not requiring supplemental oxygen – no longer requires ongoing medical care; • Not hospitalized, limitation on activities and/or requiring home oxygen; • Not hospitalized, no limitations on activities. Recovery is evaluated up until Day 29.
Key Secondary	
To evaluate the clinical efficacy of different investigational therapeutics relative to the control arm in adults hospitalized with COVID-19 according to clinical status (8-point ordinal scale) at Day 15	
 • Death; • Hospitalized, on invasive mechanical ventilation or ECMO; • Hospitalized, on non-invasive ventilation or high flow oxygen devices; • Hospitalized, requiring supplemental oxygen;

OBJECTIVES	ENDPOINTS (OUTCOME MEASURES)
	
 • Hospitalized, not requiring supplemental oxygen – requiring ongoing medical care (COVID-19 related or otherwise); • Hospitalized, not requiring supplemental oxygen – no longer requires ongoing medical care; • Not hospitalized, limitation on activities and/or requiring home oxygen; • Not hospitalized, no limitations on activities.
Additional Secondary	

To evaluate the clinical efficacy of different investigational therapeutics as compared to the control arm as assessed by:
 
 • Clinical Severity 
 ○ Ordinal scale: 
 ▪ Time to an improvement of one category and two categories from Day 1 (baseline) using an ordinal scale. ▪ Subject clinical status using ordinal scale at Days 3, 5, 8, 11, 15, 22, and 29. ▪ Mean change in the ordinal scale from Day 1 to Days 3, 5, 8, 11, 15, 22, and 29. 	
 • Clinical outcome assessed using ordinal scale daily while hospitalized and on Days 15, 22, and 29.

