8.1.2.2 Ordinal Scale

The ordinal scale is the primary measure of clinical outcome.

The scale used in this study is as follows (from worst to best):

- Death;
- Hospitalized, on invasive mechanical ventilation or ECMO;
- Hospitalized, on non-invasive ventilation or high flow oxygen devices;
- Hospitalized, requiring supplemental oxygen;
- Hospitalized, not requiring supplemental oxygen – requiring ongoing medical care (COVID-19 related or otherwise);
- Hospitalized, not requiring supplemental oxygen – no longer requires ongoing medical care;
 - This would include those kept in hospital for quarantine/infection control, awaiting bed in rehabilitation facility or homecare, etc.
- Not hospitalized, limitation on activities and/or requiring home oxygen;
- Not hospitalized, no limitations on activities

To determine a subject's clinical status using the ordinal scale: On Day 1, report their clinical status at randomization. As there should be <24 hours between randomization and infusion, the ordinal scale at done at randomization suffices as the Day 1 ordinal scale. After Day 1, collect the ordinal scale daily while hospitalized from Day 2 through Day 29 by providing the worst clinical assessment for the previous day (i.e., midnight to midnight; 00:00 – 23:59 (24-hr clock)). For those who are discharged prior to Day 15, collect ordinal scale on follow-up Days 15, 22 and 29 by providing the worst clinical assessment for the previous day (i.e., midnight to midnight; 00:00 – 23:59 (24-hr clock)). For example, on study Day 3 when completing the form, the worse

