3.3.2. Recovery and Time to Recovery

The primary efficacy outcome measure is the time to recovery. Recovery will be defined as having a value of 1, 2, or 3 on the clinical status 8-point ordinal scale. The time to recovery will be defined as the elapsed time (in days) from randomization to the earliest day at which a subject

reaches recovery. Note that since clinical status assessments are recorded as defined in Section 4.3, the day that is being assessed (not necessarily the day the response is collected) will be used to determine the timing of events. For example, a subject with a score of 5 recorded on Days 1 - 3 and a score of 3 recorded on Day 4 will have a time to recovery equal to 3 days. It is also possible that a subject has a clinical status score > 3 reported for a particular day but was subsequently discharged on the same day. Such cases will be reviewed by the NIAID Medical Officer to make the determination of whether the subject should be considered recovered in analyses. Subject data to be reviewed as part of this determination will include the reported clinical status scores while hospitalized, where the subject was discharged to (e.g. private residence, rehabilitation facility, long-term care/nursing home), and any information regarding readmittance.

Any subjects that are lost to follow-up or terminated early prior to an observed recovery will be censored at the day of their last observed assessment. Subjects who complete follow-up but do not experience recovery will be censored at the day of their Day 29 visit. All deaths within Day 29 (and prior to recovery) will be considered censored at 28 days. Note that we do not expect many subjects to worsen after discharge.

However, we will evaluate whether any discharged subjects subsequently experience a worse clinical status and sensitivity analyses will be conducted accordingly. For these analyses, subjects who recover but are later re-admitted for COVID-19 will not be considered a recovery but will instead be censored at 28 days.

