4.2.3. Method of Assigning Subjects to Treatment Groups (Randomization)

Enrollment and randomization of subjects is done online using the enrollment module of Advantage eClinical[®].

Eligible subjects will be randomized and assigned in a 1:1 ratio to either baricitinib + remdesivir or remdesivir, with stratification by site and disease severity by ordinal scale (Moderate disease [4 or 5 on the ordinal scale] or Severe disease [6 or 7 on the ordinal scale]). The randomization is based on a variable blocked scheme to provide an approximately balanced allocation to the treatment groups during the study. If arms are added or removed later in the study, randomization will continue in an equal allocation manner.

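### The protocol's Moderate stratum literally includes patients already in ordinal category 3, a recovery category, while the SAP assumes every baseline score is 4 to 7

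*Protocol*

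**What the plan says.** **Stratum.** Protocol Appendix B 6.3.1 stratifies by site and by ordinal-scale severity at enrollment. The second Moderate bullet is "Hospitalized, not requiring supplemental oxygen", with no qualifier about medical care. The ordinal scale in Appendix B 8.1.2.2 has two categories that begin this way: one for patients who still need care (numbered 4 in the SAP) and one for patients who no longer do (3). Of the latter the protocol adds: "This would include those kept in hospital for quarantine/infection control, awaiting bed in rehabilitation facility or homecare, etc".

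**Entry.** Inclusion criterion 6 in Appendix B 5.1 is met by any one of four findings, the first being "Radiographic infiltrates by imaging (chest x-ray, CT scan, etc.), OR". No criterion in 5.1 or 5.2 mentions the ordinal score. The nearest exclusion is "Anticipated discharge from the hospital or transfer to another hospital which is not a study site within 72 hours".

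**Endpoint.** Appendix B section 3 states: "Day of recovery is defined as the first day on which the subject satisfies one of the following three categories from the ordinal scale". SAP 3.3.2 agrees: "Recovery will be defined as having a value of 1, 2, or 3 on the clinical status 8-point ordinal scale". Time runs from randomization, and the Day 1 score is the status at randomization (Appendix B 8.1.2.2; SAP 4.3). Neither document requires a non-recovered baseline.

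**SAP.** Section 4.2.3 gives "Moderate disease [4 or 5 on the ordinal scale", with Severe as 6 or 7. Section 6.4 lists baseline scores 4, 5, 6 and 7 only, and protocol Appendix B 9.4.7 contrasts 4/5 with 6/7. SAP 4.2 refers eligibility back to the protocol.

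**The concern.** The two documents describe different Moderate strata, and the difference is a group of patients who have already had the primary event. A PCR-positive patient with infiltrates, breathing room air and held in hospital only for quarantine or a rehabilitation bed can satisfy the protocol's criteria and fits its Moderate bullet. Under the endpoint definition that patient has recovered at or about time zero, whichever arm is assigned.

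The primary analysis is by intention to treat on all randomized subjects (SAP 6.3.1), so the patient stays in. The patient would count as one of the approximately 723 recoveries that end accrual (Appendix B 9.2; SAP 5) and as one unit of r in the information fraction r/723 (SAP 6.6.2), displacing a recovery that could tell the arms apart. The patient would also have no place in the SAP's actual-severity or baseline-score groupings.

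**Working it through.** **1. Does the text allow it?**

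- Stratum: the bullet stops before the words that separate category 4 from category 3, so it covers both.
- Inclusion 6: infiltrates alone are enough.
- Exclusion 6: it turns on expected discharge or transfer within 72 hours. Category 3 names people held for non-medical reasons, who may stay longer. This narrows the gap but does not close it.
- Endpoint: the first day in category 3, 2 or 1, timed from randomization, with no condition on the baseline score.

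So a category 3 patient expected to stay more than 72 hours is not excluded.

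**2. The plan's own figures.** Inputs from Appendix B 9.2 and SAP 5: ratio 1.25, two-sided 5%, 85% power, 70% recovering.

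- E = 4(1.96 + z_β)² / (ln 1.25)². With z_β = 1.0364 this is 721.3. With z_β rounded to 1.04 it is 4 × 9 / 0.04979 = 723. The stated 723 reproduces.
- 723 / 0.70 = 1032.9, against the stated 1032.
- Power at 723 events: E[Z] = √723 × ln(1.25) / 2 = 3.00, and Φ(3.00 − 1.96) = 85.1%.

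**3. Effect of time-zero recoveries.** In the log-rank formula of SAP 8.1.1, a recovery at time zero under 1:1 allocation adds an expected 0 to the numerator and about 1/4 to the variance. Let q be the share of the 723 recoveries that were in category 3 at baseline. Then

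E[Z] = (1 − q) × √723 × ln(1.25) / 2 = 3.00(1 − q),

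power = Φ(E[Z] − 1.96), and the diluted ratio is about exp{(1 − q) ln 1.25}.

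| q (assumed) | Recoveries affected | E[Z] | Power | Ratio |
|---|---|---|---|---|
| 0 | 0 | 3.00 | 85.1% | 1.25 |
| 2% | 14 | 2.94 | 83.6% | 1.244 |
| 5% | 36 | 2.85 | 81.3% | 1.236 |
| 10% | 72 | 2.70 | 77.0% | 1.222 |

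**4. The denominator matters.** If the assumed share refers to the 1032 enrolled instead, it is a larger share of the events. For example, 5% of 1032 is about 52 patients, and 52/723 = 7.1%. Shares of 2%, 5% and 10% of those enrolled give power of about 83.0%, 79.6% and 73.0% when accrual stops at 723 recoveries. An unstratified log-rank simulation (exponential recovery, 1,500 runs per scenario, N fixed at 1032) gave 85.6% at 0%, 81.3% at 5% and 73.9% at 10%. These are consistent with the approximation, given that fixing N lets the total number of recoveries rise above 723.

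**5. Type I error.** Under the null hypothesis, randomization makes baseline category 3 equally likely in both arms, so the test keeps its level.

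**The case against.** The intended range is visible. SAP 4.2.3, SAP 6.4 and Appendix B 9.4.7 all point to 4 through 7, and the amendment history says the strata were revised to match the ordinal categories. The bullet can fairly be read as shorthand for category 4. The randomization procedure is deferred to the manual of procedures, and sites already need the ordinal score to randomize (Appendix B 8.1.1), so a check may already exist. Exclusion 6 leaves only longer-stay category 3 patients, and at a 2% share the loss is about 1.5 percentage points of power. All of this stands, and it makes the point a protocol-SAP inconsistency. It does not remove it: eligibility is set by the protocol, and the protocol sets no limit on the ordinal score.

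A reader might infer more than the documents support:

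- *That such patients were enrolled, or that the design meant to admit them.* Nothing shows either.
- *That ACTT-2 dropped a safeguard from ACTT-1.* The ongoing-care wording in Appendix A 1.1 and 4.1 defines an additional analysis subgroup. ACTT-1's randomization strata (Appendix A 6.3) rested on oxygen saturation, respiratory rate and respiratory support, with no ongoing-care wording.
- *That a baseline-3 subject has no severity category at all in the SAP.* SAP 6.3.1 classifies intention-to-treat analyses by randomized stratum, so the subject has a place in the primary test. Table 50 also leaves room for other baseline scores. What is missing is a place in the actual-severity groups, which the As Treated safety tables use, and in the baseline-score subgroups.

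**Conclusion.** The inconsistency is real and should be fixed, but it does not threaten the validity of the primary test. Read literally, the protocol lets patients who already meet the recovery definition be randomized as Moderate, while the SAP has no actual-severity or baseline-score group for them.

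The harm is dilution toward a ratio of 1 and some loss of power, with no inflation of the type I error rate. Its size rests wholly on an assumed share: about 84%, 81% or 77% power if 2%, 5% or 10% of the 723 recoveries were in category 3 at baseline, against 85% planned. The true share could be zero. Confidence is high about the gap in the text and low about how often it operates.

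**What to change.** 1. In Appendix B 6.3.1, complete the last Moderate bullet with the qualifier that the patient requires ongoing medical care, so that Moderate means ordinal 4 or 5 as in SAP 4.2.3.
2. In Appendix B 1.1 and 5.1/5.2, state that the ordinal score at randomization must be 4, 5, 6 or 7.
3. Enforce this with an edit check in the randomization system on the score sites already enter.
4. If any baseline-3 subjects have been enrolled, keep them in the intention-to-treat primary analysis and add a sensitivity run without them. The baseline score is recorded at randomization, so this exclusion does not depend on outcome after assignment.

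The cost is a short protocol amendment, one system check and one extra analysis. The trial would lose at most a few patients, none of whom could have informed time to recovery.
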